Trough PD Sampling ^c		X	х	Х	х		х		Х	Refer to Appendix 2 for additional detail.
NASH/ Fibrosis Biomarkers ^c		х			х		х		х	Includes CK-18 (M30 and M65), ELF (PIIINP, TIMP-1, HA), and PRO-C3.
Intensive PK Sampling (PK/PD sub-study only)		х					Xi			Intensive PK sampling will be performed pre-dose and 1, 2, 4, 6, and 24 hours post the first dose of study drug on Week 0/Day 1, and at pre-dose and 1, 2, 4, 6, 24, 48, and 72 hours post last dose of study drug at Week 12. Patients should be instructed to hold their dose of study drug until after pre- dose and after 24-hour PK samples are collected. Refer to Appendix 2 for additional detail.
Intensive PD Sampling (PK/PD sub-study Only)		х					Xj			7α C4 and FGF19 will be collected at matching timepoints to Intensive PK sampling (above) except at Week 12 when 7α C4 and FGF19 will not be collected at 48 and 72 hours post dose. Refer to Appendix 2 for additional detail.
Clinical Laborator	y Procedure	es/Assessn	nents							
Patient Fasting	х	х	х	х	х	х	х	х	х	Patients must be in fasted state for at least 8 hours prior to blood collection and treatment administration, where applicable.

	Screening]	Freatmen	t Period ^f			Follow -Up ^b ET ^a		Notes	
Visit	Screening	Week 0	Week 2	Week 4	Week 6	Week 8	Week 12	Week 16			
Study Day		Day 1	15	29	43	57	85	113			
Schedule Window (days)	-42 days		± 3	± 3	± 3	± 3	± 3	-7 /+2		Patients discontinuing the study at any time for any reason (Early Termination) should complete the ET visit as soon as feasible and return for a Follow-Up visit 4 weeks (-7 days /+2 days) after the last dose of study drug.	
Chemistry ^e	x	x	x	x	x	x	x	x	X	Specific analytes are listed in Appendix 1. ALT and AST stability may be evaluated prior to randomization per Section 5. Increased monitoring criteria for elevated ALT and/or AST above 2×Baseline or above 5×ULN, and elevated ALP above 3×ULN are outlined in Appendix 3. A standard lipid test will be collected as part of the clinical chemistry at Screening to confirm eligibility (Appendix 1). During study treatment, lipid parameters for PD assessments listed in Table 9 of Appendix 2 will be collected and results will be blinded. HDL will remain unblinded and will be collected as part of clinical chemistry at all visits. Refer to Appendix 5 for the eGFR formula, to be calculated by central lab.	
Hematology ^c	х	Х	х	Х	Х	Х	Х	Х	x	Specific analytes are listed in Appendix 1.	

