Currently, there are no warnings, precautions, or contraindications with the use of TERN-101. Embryofetal development studies have not been conducted, and TERN-101 has not been administered to pregnant or breastfeeding women. The risks of TERN-101 to the fetus or neonate are unknown, and TERN-101 should not be administered to pregnant or lactating patients or patients of childbearing potential who are not following protocol-specified contraception requirements.

Risks Relevant to TERN-501+TERN-101 Combination

An overview of clinical risks potentially anticipated for TERN-501 and TERN-101 individually is presented above. Data from the TERN-501+TERN-101 DDI cohort of the FIH Study TERN501-1009 indicate that exposures of TERN-501 and TERN-101 when administered in combination are expected to be comparable to exposures of the individual agent when administered alone. Nonclinical safety studies overall support that dosing of TERN-501 and TERN-101 in combination is unlikely to produce unique risks beyond those of the individual agents.

The combination of TERN-501+TERN-101 is not anticipated to change any potential for central thyroid axis modulation relative to TERN-501 alone or increase the theoretical risks for effects on cardiovascular or skeletal systems due to systemic thyroid hormone stimulation. The combination of TERN-501+TERN-101 is also not anticipated to change any potential for TERN-101 effects on sex hormone levels.

There is the possibility that combining TERN-501 and TERN-101 could potentially offset adverse effects from each individual agent. For example, the anticipated LDL cholesterol lowering effect from THR- β agonism may mitigate risk of LDL cholesterol increase associated with FXR agonism. However, TERN-501 is not expected to change the risk of HDL cholesterol reduction by TERN-101.

Although elevation of liver enzymes has been reported with FXR and THR- β agonists (Mudaliar 2013; Lian 2016; Sjouke 2014), evidence of drug-induced liver injury has not been observed with

TERN-501 or TERN-101 and there is no expectation for liver enzymes to worsen with the combination of TERN-501+TERN-101 compared to either agent administered alone based on available data.

Finally, the administration of TERN-501+TERN-101 is not anticipated to change the potential for pruritus associated with TERN-101.

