Exploratory Objectives	Exploratory Endpoints		
 To explore the effect of TERN-501 monotherapy on efficacy and markers of target engagement compared to placebo To explore the effect of TERN-501+TERN- 101 on efficacy and markers of target engagement, compared to placebo and/or each monotherapy 	 Change from baseline in the following parameters, as applicable: ALT, AST, and GGT FIB-4, CK-18 (M30 and M65), ELF (PIIINP, TIMP-1, HA), PRO-C3, and FAST score TE and CAP MRI-PDFF (relative change) and cT1 SHBG Lipid panel (for PD as well as safety evaluation) rT3 FGF19, bile acids, and 7αC4 Proportion of responders on MRI-PDFF and/or cT1 with the following: ≥ 30% relative reduction in MRI-PDFF ≥ 80 msec reduction in cT1 		
• To evaluate the pharmacokinetics of TERN-501 and TERN-101 administered alone and in combination	• PK parameters (e.g., AUC, C _{max} , C _{tau})		

Abbreviations: $7\alpha C4 = 7\alpha$ -hydroxy-4-cholesten-3-one; ALT = alanine transaminase; AST = aspartate transaminase; AUC = area under the concentration-time curve, CAP = controlled attenuation parameter; CK-18 = cytokeratin-18; C_{max} = maximum observed concentration; cT1 = corrected T1; C_{tau} = concentration at the end of the dosing interval; ELF = enhanced liver fibrosis; FAST score = FibroScan AST score; FGF19 = fibroblast growth factor-19; FIB-4 =

Protocol TERNCB-2002 Terns, Inc.

fibrosis-4; GGT = gamma-glutamyl transferase; HA = hyaluronic acid; MRI = magnetic resonance imaging; MRI-PDFF = magnetic resonance imaging proton density fact fraction; PIIINP = procollagen III N-terminal propeptide; PD = pharmacodynamics; PK = pharmacokinetics; PRO-C3 = released N-terminal pro-peptide of type III collagen; rT3 = reverse T3; SHBG = sex hormone binding globulin; TIMP-1 = tissue inhibitor of metalloproteinases-1; TE = transient elastography

4. Study Design

4.1. **Overall Design**

This study is a multicenter, randomized, double-blind, placebo-controlled, parallel-group treatment, phase 2a study.

Approximately 140 noncirrhotic NASH patients with fibrosis identified based on prior liver biopsy and/or imaging and clinical criteria who meet study eligibility criteria will be enrolled and randomized equally into 7 groups: once daily orally administered TERN-501 1 mg (n=20), TERN-501 3 mg (n=20), TERN-501 6 mg (n=20), TERN-501 3 mg+TERN-101 10 mg (n=20), TERN-501 6 mg+TERN-101 10 mg (n=20), TERN-101 10 mg (n=20), or matching placebo (n=20).

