With the linear, dose-proportional PK demonstrated in the FIH study, dose levels of 1 mg, 3 mg, and 6 mg are expected to provide 2- to 3-fold differences in exposures with minimal overlap. Based on the available safety data from the FIH study and $a \ge 6$ -fold margin relative to the NOAEL in dogs, the more sensitive toxicology species, all doses selected are expected to have an acceptable safety margin in NASH patients in this 12-week study (see Section 2.2.2.1.2.1). As such, the safety, PK, and PD data support the selection of 1 mg, 3 mg, and 6 mg doses of TERN-501 for the monotherapy arms of this study.

TERN-101 Dose Rationale:

A dose level of 10 mg TERN-101 once daily was selected to be administered in combination with TERN-501, and as a monotherapy control, based on efficacy, safety, PK, and PD data. TERN-101 has been evaluated at doses of 5 mg, 10 mg, and 15 mg once daily in NASH patients for 12 weeks in a phase 2a study (Study TERN101-2001). Overall, TERN-101 was generally

safe and well-tolerated at all dose levels studied. Pruritus was observed in 11.5% of patients who received 10 mg TERN-101 in the study; all pruritus AEs were mild or moderate and did not result in study or treatment discontinuation. LDL cholesterol changes with 10 mg TERN-101 were not statistically different from placebo during the 12 weeks of treatment. Transient reductions in HDL cholesterol were seen in the 10 mg group at Week 4 through Week 8, but percent change from baseline for 10 mg TERN-101 was not statistically different from placebo at Week 12. TERN-101 10 mg reduced ALT, GGT, MRI-PDFF, and cT1. The effects of TERN-101 on 7 α C4, a marker of FXR target engagement, appeared to plateau at the 10 mg dose, suggesting maximal or near maximal target engagement was achieved at 10 mg. Additionally, safety, pharmacology, and toxicology studies support the continued study of TERN-101 at 10 mg (see Section 2.2.2.1.2.1). Thus, balancing the potential for efficacy with the overall safety profile, 10 mg TERN-101 was selected as the optimal dose to combine with TERN-501 and as a monotherapy comparator arm.

TERN-501 Dose Rationale in Combination with TERN-101 10 mg:

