9.4.4.3. Pharmacodynamic Endpoints

PD markers of THR- β agonism include SHBG and lipids, while PD markers of FXR agonism include FGF19, 7 α C4, and bile acids. Descriptive statistics of PD marker results, change from baseline, and percent change from baseline will be summarized by treatment group and visit. Change (and separately percent change) from baseline will be analyzed at applicable time points using the same ANCOVA model specified for the primary endpoint.

Pharmacodynamic parameters may also be calculated, summarized, and described by plotting the concentration-time curve or time-effect curve.

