The tests detailed in Table 9 will be performed by the central laboratory, as specified in the Schedule of Activities. The exact times of blood sampling will be recorded in the eCRF.

Table 9PD Laboratory Assessments

PD Assessments	Parameters	
Lipid Panel	Total cholesterol	apo B
	Triglycerides	apo Al
	LDL cholesterol	Lipoprotein(a)
	VLDL	
	Non-HDL cholesterol	
	LDL particle number	
SHBG, 7αC4, FGF19, bile acids	SHBG, 7αC4, FGF19, bile acids	

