8.3. Clinical Safety Laboratory Evaluations

All laboratory assessments are specified in Appendix 1 of the study protocol. Laboratory parameters will be summarized in conventional units. Coagulation parameters, hemoglobin A1c, direct bilirubin, and indirect bilirubin will not be summarized.

Quantitative clinical chemistry, hematology, and urinalysis results will be summarized by treatment group using descriptive statistics at baseline and at each post-baseline visit. The change and percent change from baseline will also be summarized.

Additional summaries will be provided by scheduled visits for the number and percentage of patients with

- Total CK > 5x ULN
- Hg < 10 mg/dL
- HCT < 30%
- platelets < 100,000 /microL
- WBC < LLN

All clinical safety laboratory data will be presented in by-patient data listings. A separate listing for central laboratory normal ranges, by lab category, lab test, lab parameter, sex, and age, will be presented.

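### HDL cholesterol, an anticipated TERN-101 effect, has no planned baseline-adjusted difference from placebo with a CI: the SAP models only LDL-c among the lipids, and the lipid safety section it cites does not exist.

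*Protocol*

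**What the plan says.** **Collection.** HDL is listed among the lipid tests in clinical chemistry (Protocol Appendix 1, Table 7). The schedule (Protocol Section 1.3) states: "HDL will remain unblinded and will be collected as part of clinical chemistry at all visits". The PD lipid panel (Protocol Appendix 2, Table 9) includes "Non-HDL cholesterol" but not HDL itself.

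**Expected effect.** Protocol Section 2.3: "TERN-501 is not expected to change the risk of HDL cholesterol reduction by TERN-101". Protocol Section 4.3, on the earlier 12-week TERN-101 study: "Transient reductions in HDL cholesterol were seen in the 10 mg group at Week 4 through Week 8". The same sentence adds that the 10 mg group did not differ statistically from placebo at Week 12.

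**Protocol analysis.** Section 9.4.4.3 says that PD markers of THR-β "agonism include SHBG and lipids, while PD markers of FXR agonism include FGF19", among others. It continues: "Change (and separately percent change) from baseline will be analyzed at applicable time points using the same ANCOVA model specified for the primary endpoint". In Section 3 the lipid panel is an exploratory endpoint that serves both PD and safety evaluation.

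**SAP analysis.**
- Section 7.18 applies the Section 7.7 ANCOVA to SHBG and LDL-c. It names no other lipid for modelling.
- Section 8.3: "Quantitative clinical chemistry, hematology, and urinalysis results will be summarized by treatment group using descriptive statistics at baseline", and at each post-baseline visit, together with change and percent change.
- Section 8.3.5 adds tables of shifts from normal at baseline to abnormal, for each chemistry test and visit.
- Section 5 restricts the baseline-statin subgroup to a safety analysis of lipids, which it locates in Section 8.3.3. Section 8.3.3 is Sex Hormones.
- Sections 8.3.2 and 8.3.3 give thyroid tests and sex hormones LS mean differences with 95% CIs.
- Section 10 declares no changes from the protocol analyses.

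**The concern.** The protocol weighs two lipid effects of the combination together in Section 2.3. LDL cholesterol may improve because TERN-501 lowers it, while the HDL risk from TERN-101 is expected to remain. The SAP gives the first a modelled difference from placebo with an interval, and the second only arm-by-arm summaries. Three of the seven arms receive TERN-101 (3 × 20 = 60 of 140 planned patients), and safety of the combination is a secondary objective.

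The earlier HDL findings for TERN-101 (Protocol Sections 2.2.2.2, 2.3 and 4.3) were themselves reported against placebo, so this trial would not produce a planned estimate of the same kind. The SAP already models selected safety analytes. Its pointer to a lipid safety section suggests that such an analysis was at least considered.

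**Working it through.** The plan gives no HDL figure to reproduce. Its sample-size section covers only MRI-PDFF and cT1. The check is mainly a tracing of which analysis reaches HDL, followed by a short precision calculation.

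**1. Which planned analysis covers HDL?**

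| Place | Method | Covers HDL? |
|---|---|---|
| Protocol 9.4.4.3 | ANCOVA of PD markers, including lipids | Can be read in; not named |
| SAP 7.18 | Section 7.7 ANCOVA | No: SHBG and LDL-c only |
| SAP 8.3 | Descriptive level, change, percent change by arm and visit | Yes, as chemistry |
| SAP 8.3.5 | Normal-to-abnormal shifts by visit | Yes, as chemistry |
| SAP 8.3.2, 8.3.3 | LS mean differences, 95% CI | No: thyroid, sex hormones |
| Lipid safety section cited in SAP 5 | Not written | – |

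No row gives a baseline-adjusted HDL difference from placebo with a CI. The shift tables do not fill the gap: they do not count a fall within the normal range, or a further fall in a patient already abnormal at baseline.

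**2. Would restoring the full PD panel to the model be enough?** No. Table 9 omits HDL, so extending SAP 7.18 from LDL-c to the whole panel would still leave it out. HDL has to be named.

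**3. What would baseline adjustment add in precision?** Inputs: 20 per arm and seven arms (Protocol Section 9.2), a complete-data calculation. The baseline-to-visit correlation r is not in the documents; I assume 0.6 to 0.8. With equal variances at baseline and visit (SD = 1):
- variance of absolute change = 2(1 − r)
- ANCOVA residual variance = 1 − r²
- SE ratio, ANCOVA to change = √[(1 − r²) / (2(1 − r))] = √[(1 + r)/2]
- 95% half-width, change score = t(0.975, 38) × √[2(1 − r)] × √(2/20)
- 95% half-width, ANCOVA = t(0.975, 132) × √(1 − r²) × √(2/20), with 140 − 7 − 1 = 132 df

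| r | SE ratio | SE reduction | Half-width, change | Half-width, ANCOVA |
|---|---|---|---|---|
| 0.6 | √0.80 = 0.89 | 11% | 0.573 | 0.500 |
| 0.7 | √0.85 = 0.92 | 8% | 0.496 | 0.447 |
| 0.8 | √0.90 = 0.95 | 5% | 0.405 | 0.375 |

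Half-widths are in units of the raw HDL SD. They also reflect the larger df of the seven-arm model, so they shrink slightly more than the SE. Over a wider assumed range, r = 0.5 to 0.9, the variance reduction runs from 25% to 5%.

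**4. How many intervals would this create?** Six active arms × five visits = 30. If no arm affected HDL, about 30 × 0.05 = 1.5 would be expected to exclude zero by chance.

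**The case against.** The strongest reply is that descriptive reporting of safety laboratories is what Protocol Section 9.4.5 plans, and that the secondary safety endpoint is adverse-event incidence. SAP Section 8.3 tabulates HDL at Weeks 4 and 8 beside a concurrent randomised placebo arm. From the n, mean and SD shown for each arm, a reader could form an unadjusted difference and interval. Protocol Section 2.2.2.2 also says that TERN-101 doses below 15 mg gave no clinically meaningful or sustained adverse lipid change over 12 weeks. All of this stands. It limits the size of the point, but it does not supply a planned, adjusted estimate.

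Four stronger readings are tempting, and the documents do not support them:
- **That HDL goes unmodelled because it is outside Table 9.** Total cholesterol, triglycerides, apo B and apo A1 are in Table 9 and are not modelled either. Thyroid tests and sex hormones are outside it and are. The direct causes are SAP 7.18 and the missing lipid safety section.
- **That the protocol's model cannot reach HDL.** Section 9.4.4.3 speaks of lipids without limiting them to Table 9.
- **That a Week 4 to 8 effect would be missed because only the end of treatment is read.** Every post-baseline visit is summarised.
- **That the separate LDL bands in SAP 8.3.1 show HDL was neglected.** The SAP explains them by LDL not being gradable under CTCAE version 5.

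**Conclusion.** The concern holds as an estimation gap in the SAP. The protocol anticipates an HDL reduction with TERN-101 and plans ANCOVA for lipids. The SAP narrows lipid modelling to LDL-c and cites a lipid safety section that was not written. As a result, no baseline-adjusted HDL difference from placebo with a CI is planned.

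The size is modest. The main gain is a pre-specified controlled estimate at the visits where the earlier 10 mg effect appeared. The precision gain is about 5 to 11% in the SE of absolute change, which rests on the assumed correlation of 0.6 to 0.8 and equal variances. A reader might infer that a clinically important HDL harm at 10 mg is established; the protocol's account of the earlier study says otherwise. The primary endpoint and its power are not affected.

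**What to change.** In SAP Section 8.3, or in a restored lipid safety subsection:
1. Name HDL cholesterol explicitly.
2. Analyse absolute change from baseline with the Section 7.7 ANCOVA (treatment plus baseline) on the Safety set. Give the LS mean difference from placebo, SE and 95% CI for each active arm at Weeks 2, 4, 6, 8 and 12, labelled nominal and descriptive. State the visits, because Section 7.7 defaults to Week 12 for the Table 6 comparisons. SAP Table 4 already defines chemistry windows for all five.
3. Present percent change as LS means with SE and 95% CI only. Section 7.7 reserves inference on relative change for MRI-PDFF, so percent-change comparisons should not be added here.
4. Correct the Section 5 cross-reference to the lipid safety analysis.

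The cost is one extra table from an existing model, using data already collected, and 30 nominal intervals without multiplicity adjustment. These should be read as a pattern across visits and arms, not one by one.

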2.1. Overview of Non-alcoholic Steatohepatitis (NASH) and Unmet Need

This study is a randomized, double-blind, placebo-controlled, parallel-group treatment, phase 2a study to evaluate the safety, efficacy, pharmacokinetics, and pharmacodynamics of orally administered TERN-501 as monotherapy and in combination with TERN-101 in noncirrhotic adult patients with presumed NASH.

NAFLD is characterized by an excessive accumulation of fat deposits in liver tissue, commonly associated with co-morbidities such as obesity, diabetes mellitus, and dyslipidemia, in the absence of secondary causes of liver fat accumulation. NASH, an advanced form of NAFLD, is defined by the presence of hepatic inflammation and hepatocellular ballooning, with or without fibrosis, in the setting of underlying hepatic steatosis. Progression from NAFLD to NASH can be rapid and, with progression, NASH can lead to cirrhosis, decompensated liver disease, and increased risk for hepatic carcinoma and liver-related mortality (Ekstedt 2015). Complications from end-stage liver disease (e.g., jaundice, edema, ascites, portal hypertension, coagulopathy, hepatic encephalopathy) are challenging to manage and may require liver transplantation. NASH was recently identified as the second leading etiologic indication for liver transplantation in the United States (US), and it is projected to become the leading cause of liver transplantation in the coming years (Wong 2015). Patients with NAFLD have a 7-fold increased risk of mortality from hepatocellular carcinoma compared with a matched reference population (Ekstedt 2015).

NAFLD is the most common cause of chronic liver disease in North America (Chalasani 2018), and its prevalence of NAFLD is steadily increasing with the aging population and cardiovascular and endocrine comorbidities associated with obesity, (e.g., atherosclerosis, insulin resistance/diabetes mellitus) (Dietrich 2014, Lonardo 2018, Andronescu 2018). Approximately 30% of patients with NAFLD may progress to NASH. Currently, there are no approved therapies for NASH. Therapeutic options are limited to management of comorbidities such as hyperlipidemia, insulin resistance/diabetes, and obesity, with weight loss through diet and exercise as a key treatment for NASH (Chalasani 2018). However, many patients are unable to comply long-term with the required dietary and lifestyle changes. For advanced fibrosis, cirrhosis, and hepatocellular carcinoma, liver transplantation may be the only treatment option. A therapeutic agent that addresses NASH would offer a significant advancement for this unmet medical need.

2.2. Background

2.2.1. THR-β Agonism and TERN-501 for Treatment of NASH

THR- β is the major form of thyroid hormone receptor in the liver, where it plays an important role in energy metabolism, with stimulation of THR- β leading to liver fat and serum lipids

reduction (Taub 2013; Harrison 2019). Thyroid hormone regulates metabolism by modulating gene expression directly and through crosstalk with other nuclear hormone receptors (Liu 2010).

Thyroid hormone agonism was initially explored for treatment of dyslipidemia using first generation agents such as eprotirome and sobetirome (Zucchi 2020). Eprotirome, a modestly selective THR-β agonist, reduced LDL cholesterol when added to conventional statin therapy, but led to increased liver enzymes in a phase 3 trial (Sjouke 2014). Other earlier agonists with modest THR-ß selectivity, led to concerns of bone loss (Ladenson 2010) and cardiac toxicity (Coronary Drug Project 1972). Currently, two synthetic THR-β selective agonists are in clinical development for NASH, resmetirom (MGL-3196, Madrigal Pharmaceuticals) a liver-directed, orally active agonist of THR-β, and VK2809 (MB07811, Viking Therapeutics), a cvtochrome P450-activated prodrug. Resmetirom improved lipid parameters, reduced liver fat, and improved histologic measures of NASH on liver biopsy over 36 weeks, with an overall reassuring safety profile (Harrison 2019). VK2809 reduced cholesterol and both serum and hepatic triglycerides at doses that were sparing of cardiac toxicity and did not affect body or heart weight, glycemia, or the thyroid hormone axis in animal models (Erion 2007). Preliminary clinical study data indicates that VK2809 reduced liver fat content and improved lipid profiles over 12 weeks of treatment with no noted safety concerns (Loomba 2019); however, increases in mean ALT in a dose-dependent fashion over 14 days of dosing in healthy volunteers have been reported (Lian 2016).

TERN-501, a novel thyroid hormone analogue, is being developed for NASH. TERN-501 has a 23-fold selectivity for THR- β over THR- α in vitro and shows enhanced liver distribution. In a rat distribution study, TERN-501 concentrations in the liver were 2.5-fold higher than in plasma and kidney, and 16-fold higher than in the heart. With high selectivity for THR- β over THR- α and enhanced liver distribution, TERN-501 may offer NASH patients an important treatment option. In the FIH study (Study TERN501-1009), single doses up to 60 mg and once daily doses up to 10 mg for 14 days were assessed in healthy subjects with mildly elevated LDL cholesterol. TERN-501 was overall safe and well-tolerated with a favorable PK profile and demonstrated significant increases in SHBG, a key marker of hepatic THR- β engagement and significant reductions in LDL cholesterol and other lipid parameters, supporting further investigation of TERN-501 in patients with NASH (See Section 2.2.1.2). Detailed background on thyroid hormone and the potential role of THR- β selective agonism and TERN-501 in NASH are provided in the Investigator's Brochure.

[figure not shown]
